11.0 STATISTICAL AND ETHICAL CONSIDERATIONS

11.1 **Sample Size and Study Duration**

APEC1621G will require a minimum of 20 evaluable patients and a maximum of 49 patients, allowing for 15% inevaluability. Assuming an enrollment rate of 6-15 biomarker positive patients per year, the primary cohort of this subprotocol is expected to be completed within 1.6-4 years.

11.2 **Dosing Considerations**

Vemurafenib will be given at 550 mg/m²/dose (adult MTD equivalent) orally BID continuously; capped at the adult MTD of 960 mg/dose; one cycle will be 28 days. This is the likely pediatric MTD/RP2D to be recommended from the pilot dose finding study of vemurafenib for children with relapsed or refractory BRAFV600E mutant gliomas (NCT01748149). The dosing nomogram is in [Appendix IV-A](#) and [Appendix IV-B](#).

11.3 **Study Design**

The primary cohort will employ a single stage A'hem design of N=20. The agent will be deemed worthy of further study in the relevant subset of patients (i.e. biomarker positive in any histology, biomarker positive in a particular histology, etc) if the decision rule is met. Operating characteristics are shown below.

Cohort	N	Decision Rule	Alpha	Power
Primary biomarker positive	20	≥ 3 responses	10%	90%

Histology-specific biomarker positive expansion cohorts will, by definition, be deemed worthy of further study, since they will have at least 3 responses. The table below shows 90% confidence intervals (Wilson method) for a range of observable response rates.

Cohort Size	Observed Response Rate	90% Confidence Interval
10	30%	13% - 56%
10	40%	19% - 65%
10	50%	27% - 73%

11.3.1 **Primary Cohort:**

APEC1621G will evaluate a primary cohort of 20 mutation-matched (“biomarker positive”) evaluable patients of any histology for the primary study aim of determining the objective response rate (CR/PR according to the response criteria in [Section 12.3](#)) to the agent. Using an A’Hern design⁴⁰ with alpha=10%, a sample of N=20 will provide 90% power to detect an improvement in response rate from 5%, if the treatment is ineffective, to 25% if the targeted therapy is sufficiently effective to warrant further study. If there are at least 3 responses out of 20 in the primary cohort, the biomarker/therapy match will be deemed a success.

11.3.2 **Histology-Specific Biomarker Positive Expansion Cohorts:**

If ≥ 3 patients in the primary cohort with the same histology show signs of objective response (CR/PR according to the response criteria in [Section 12.3](#)), a histology-specific biomarker positive expansion cohort will open after the primary cohort is completed to up to 7 evaluable patients for a total sample size of 10 evaluable biomarker positive patients with that histology. This will allow us to estimate more precisely the activity in biomarker positive patients of that histology. See [Appendix VI](#) for a list of target tumor histologies.

We will open up to 3 such expansion cohorts for biomarker positive patients (i.e., if 3 histologies have ≥ 3 responses, we will open a total of 3 expansion cohorts as described above). Note that this can only happen if the response rate in the primary cohort is at least 45% (9/20) and there cannot be more than 21 additional evaluable patients in total for these expansion cohorts.

11.4 **Methods of Analysis**

Response criteria are described in [Section 12](#). A responder is defined as a patient who achieves a best response of PR or CR on the study. Response rates will be calculated as the percent of evaluable patients who are responders, and confidence intervals will be constructed using the Wilson score interval method.⁴¹ Decision making for A’Hern design cohorts will follow rules described above.

Toxicity tables will be constructed to summarize the observed incidence by type of toxicity and grade. A patient will be counted only once for a given toxicity for the worst grade of that toxicity reported for that patient. Toxicity information recorded will include the type, severity, time of onset, time of resolution, and the probable association with the study regimen.

11.5 **Evaluability for Response**

Any eligible patient who is enrolled and receives at least one dose of protocol therapy will be considered evaluable for response. Any patient who receives non-protocol anti-cancer therapy during the response evaluation period will be considered a non-responder for the purposes of the statistical rule, unless they show an objective response prior to receiving the non-protocol anti-cancer therapy (in which case they will be considered a responder). Patients who demonstrate a complete or partial response confirmed by central review will be considered to have experienced a response. When opening expansion cohorts, the

evaluation period for determination of best response will be 6 treatment cycles. All other patients will be considered non-responders. Patients who are not evaluable for response evaluation may be replaced for the purposes of the statistical rule. All patients considered to have a response (CR or PR) must have imaging studies reviewed centrally at the COG. Centers will be notified by the COG about requests for scans of patients with stable disease. Preliminary assessment of activity using institutionally provided tumor measurements will be entered into CDUS quarterly. The central review by COG will be provided as the final reviewed assessment of response when such becomes available.

11.6 **Evaluability for Toxicity**

All eligible patients who receive at least one dose of protocol therapy will be considered in the evaluation of toxicity.

11.7 **Progression free survival (PFS)**

Progression free survival will be defined as time from the initiation of protocol treatment to the occurrence of any of the following events: disease progression or disease recurrence or death from any cause. All patients surviving at the time of analyses without events will be censored at their last follow-up date.

PFS along with the confidence intervals will be estimated using the Kaplan-Meier method. Patients with local calls of disease progression (i.e. calls made by the treating institution), will be counted as having had an event, even if the central review does not declare progression. We will also report PFS based on central radiology review as a secondary analysis, if adequate number of disagreements in progressions exist between the treating institutions and the central radiology review to make such an analysis meaningful.

11.8 **Correlative Studies**

A descriptive analysis of the exploratory aims described in [Section 1.3](#) will be performed and will be summarized with simple summary statistics. All of these analyses will be descriptive in nature.

11.9 **Gender and Minority Accrual Estimates**

The gender and minority distribution of the study population is expected to be:

Racial category	Ethnicity					
	Not Hispanic or Latino		Hispanic or Latino			
	Female	Male	Female	Male		
American Indian/Alaska Native	0	0	0	0	0	
Asian	1	1	0	0	2	
Native Hawaiian or Other Pacific Islander	0	0	0	0	0	
Black or African American	3	5	0	0	8	
White	12	20	3	2	37	
More than one race	1	0	1	0	2	
Total	17	26	4	2	49	

This distribution was derived from the demographic data for patients enrolled on recent COG Phase 2 trials.

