positive metastatic or unresectable papillary thyroid cancer refractory to radioactive iodine demonstrated anti-tumor activity with partial responses recorded in 10 of 26 patients.³² A phase 2 study of vemurafenib in patients with metastatic BRAF mutated colorectal cancer, however in marked contrast to melanoma patients, did not show meaningful clinical activity.³³ Only one patient out of 21 had confirmed partial response, and median progression free survival was 2.1 months. A phase 2 trial of vemurafenib in BRAF V600 mutated melanoma with brain metastases demonstrated clinically meaningful responses without significant CNS toxicity. Evaluating the intracranial best overall response rate was 18% with 2 complete responses and 14 partial responses out of 90 patients with previously untreated brain metastases.³⁴

A histology-independent phase 2 basket studies of vemurafenib in BRAF V600 mutation positive non-melanoma patients was performed.³⁵ A total of 122 patients with BRAF V600 mutation positive cancers were stratified into six pre-specified cohorts and all other tumor types were enrolled in seventh cohort. Patients were treated at the adult recommended dose of 960mg BID with the primary endpoint of response rate. The overall safety data were similar to prior studies with most common adverse event being rash (68%), fatigue (56%), and arthralgia (40%). Best responses were seen among patients with non-small cell lung cancer (42% response rate) and histiocytoses (43% response rate). V600 appears to be targetable in some but not all of the non-melanoma cancers with BRAF V600 mutations.

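### The n=10 response rate for an expanded histology includes the responders that triggered the expansion, so it is biased upward and its 90% Wilson interval can under-cover

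*Combined protocol and SAP*

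**What the plan says.** The trigger is in section 11.3.2: "If ≥ 3 patients in the primary cohort with the same histology show signs of objective response", a cohort for that histology opens once the primary cohort is complete. Up to 7 evaluable patients are added, "for a total sample size of 10 evaluable biomarker positive patients with that histology", so the primary-cohort patients of that histology, including the triggering responders, are part of the 10. The purpose is estimation: "This will allow us to estimate more precisely the activity in biomarker positive patients of that histology".

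Section 11.4 calculates the response rate as responders over evaluable patients and says that "confidence intervals will be constructed using the Wilson score interval method". It gives no confidence level. The 90% comes from section 11.3: "The table below shows 90% confidence intervals (Wilson method) for a range of observable response rates". That table uses a cohort of 10 and starts at an observed 30%.

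Section 11.3 also allows a verdict of worth for patients "biomarker positive in a particular histology" and states: "Histology-specific biomarker positive expansion cohorts will, by definition, be deemed worthy of further study, since they will have at least 3 responses". No section gives an estimate that allows for the trigger, a separate result for the added patients, or a caution about reading the n=10 figure.

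**The concern.** An ordinary binomial estimate and Wilson interval assume that the count of responders was free to take any value from 0 to 10. Here the n=10 result exists only if the first m patients of that histology already supplied at least 3 responders. Low counts are removed before the result is reported, so the rate is too high on average, and the interval is computed as if no selection had taken place.

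What is at stake is the figure that the expansion is meant to deliver. A reader shown 40% (19%-65%) for one tumour type would take it as an ordinary estimate and could plan further work on it. The plan does not require the report to say how many of the 10 came from the primary cohort, or how the later patients fared.

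**Working it through.** **Inputs.** From sections 11.3 to 11.4: trigger of at least 3 responders; total n=10; crude rate; 90% Wilson interval; target rate 25%. Assumed: m, the number of primary-cohort patients of that histology, is 3-9, because the documents give no number and at m=10 or more nothing would be added.

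**The plan's own figures.** With z=1.645, the Wilson interval is 12.7-55.8% for 3/10, 19.4-64.8% for 4/10 and 26.9-73.1% for 5/10, matching the table in 11.3. For the primary rule, P(X≥3 | 20, 5%) = 7.5% and P(X≥3 | 20, 25%) = 90.9%, consistent with the stated 10% and 90%.

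**Model.** A ~ Bin(m, p) is the number of primary-cohort responders of that histology, B ~ Bin(10−m, p) the number among added patients, and T = A + B. Everything is conditional on A≥3.

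- Mean reported rate = [E(A | A≥3) + (10−m)p] / 10. Since E(A | A≥3) exceeds mp whenever p<1, the rate is biased upward at every true rate below 100%.
- Coverage = sum of P(T=t | A≥3) over those t whose Wilson interval contains p.

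**Worked case, m=6, p=25%.** P(A=3, 4, 5, 6) = 0.1318, 0.0330, 0.0044, 0.0002, so P(open) = 0.1694. E(A | A≥3) = 0.5508/0.1694 = 3.25. The mean rate is (3.25 + 4×0.25)/10 = 42.5%. Among counts of 3 or more, only 3/10 and 4/10 give intervals containing 25%.

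- P(T=3 | open) = 0.1318×0.75⁴/0.1694 = 0.246.
- P(T=4 | open) = (0.1318×4×0.25×0.75³ + 0.0330×0.75⁴)/0.1694 = 0.390.
- Coverage is 0.246 + 0.390 = 63.6%. Unselected, counts 1 to 4 cover, giving 86.6%.

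**All m at a true 25%, given opening:**

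| m | P(open) | mean rate | coverage |
|---|---|---|---|
| 3 | 1.6% | 47.5% | 44.5% |
| 4 | 5.1% | 45.8% | 50.7% |
| 5 | 10.4% | 44.1% | 57.1% |
| 6 | 16.9% | 42.5% | 63.6% |
| 7 | 24.4% | 41.0% | 69.9% |
| 8 | 32.1% | 39.5% | 75.7% |
| 9 | 39.9% | 38.2% | 80.4% |

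**Other true rates.** Coverage moves in a saw-tooth as p crosses interval limits. The lower limit for 5/10 is 26.9%, just above 25%, so 25% lies near a trough.

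| true rate | coverage, m=4-8 | unselected |
|---|---|---|
| 25% | 51-76% | 87% |
| 27% | 77-92% | 93% |
| 43% | 73-89% | 89% |
| 50% | 84-94% | 89% |

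The 43% row is the adult histiocytosis response rate cited in section 2.3.2. At 50% with m of 6 or more, coverage is 92-94%, so there is no under-coverage.

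**Average.** Over true rates 15-50%, weighting each rate by its probability of opening, coverage is 77% (m=4) to 89% (m=8), against about 90% unselected.

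**Example.** With 3/3 in the primary cohort and then 0/7, the plan reports 3/10 = 30% (13%-56%). The added patients alone give 0/7, with a 90% Wilson interval of 0%-28%.

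**The case against.** The strongest reply is that the selection is in plain view and its effect modest where it matters. Section 11.3 says that these cohorts will have at least 3 responses and tabulates rates from 30% upward; section 11.3.2 states the trigger and the pooling. The 25% rate is the pooled any-histology alternative, not a rate for one tumour type, and it sits near a trough. Under-coverage is worst at small m and low true rates, where cohorts seldom open: m=3 opens 1.6% of the time at 25%. An equal-weight average over 15-50% would give 67-84% for m=4-8, but it overweights rates at which few cohorts open. And if unopened histologies were also reported at n=m, overall coverage at 25% would be 92-98% for m=4-8.

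Most of this stands as a limit on size. It does not remove the point: the n=10 result exists only for histologies that open, its upward bias is present at every true rate below 100%, and disclosing the floor is not the same as saying that the estimate is biased.

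A reader might also infer that the automatic verdict in section 11.3 is a decision error, since added patients cannot change it. The documents do not support that. The trigger is an openly stated criterion for further study; the worst result, 3/10, is above the 25% target; and at the 5% null rate a histology with m=3-9 triggers with probability 0.01-0.8%.

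**Conclusion.** The point holds and is minor. For any histology that expands, the planned n=10 rate cannot fall below 30% and is biased upward. Its nominal 90% interval can under-cover, mainly when m is small or the true rate is low. At a true 25% and m=4-8 the mean is 40-46% and coverage 51-76%, against 87% unselected. The opening-weighted average of about 77-89%, against about 90%, is the fairer summary of coverage.

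These figures rest on an assumed m, independent responses at one true rate within the histology, and conditioning on the cohort opening and reaching 10. It would be too strong to say that the interval always under-covers: at a true 50% with m of 6 or more it does not. Nor does the point touch the primary conclusion, since the rule of at least 3 responses in 20 keeps its exact alpha of 7.5% and power of 90.9%.

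**What to change.** Add to sections 11.3.2 and 11.4, with m defined as the number of primary-cohort patients of that histology:

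> For each expanded histology, the response rate and 90% Wilson interval in all 10 patients will be reported with m and a statement that they include the responders that triggered the expansion, so the rate is biased upward and the interval may not have 90% coverage. Beside them, the responders, rate and 90% Wilson interval in the patients enrolled after the trigger will be reported.

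The added patients' result is free of the trigger's selection, because their responses play no part in opening the cohort. The cost is a few sentences and one extra row per expanded histology, with no extra patients and no change to any decision rule.

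The downside is a wide interval when few patients are added (0/2 gives 0%-57%), so the new row should accompany the all-10 result and not replace it. A conditional maximum-likelihood estimate for all 10 is not recommended: at 3/10 it is 0% for every m from 3 to 9, despite three observed responders, and at a true 25% that count arises in 13-44% of opened cohorts. The statement in section 11.3 that expanded histologies merit further study can stay.

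### Section 11.3 declares an expansion cohort a success on the same responses that open it, so the added patients cannot change that declaration, and the pooled result of 10 carries the selecting responses

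*Combined protocol and SAP*

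**What the plan says.** All of this stands in Section 11.3 (Study Design) and its subsections 11.3.1 and 11.3.2.

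- **Scope of the verdict.** "The agent will be deemed worthy of further study in the relevant subset of patients" if the decision rule is met. The text expressly allows the subset to be one histology.
- **Primary rule (11.3.1).** The design is A'Hern: "with alpha=10%, a sample of N=20 will provide 90% power" for a rise from 5% to 25%. The match succeeds "If there are at least 3 responses out of 20 in the primary cohort".
- **Opening an expansion cohort (11.3.2).** "If ≥ 3 patients in the primary cohort with the same histology show signs of objective response", a cohort opens and takes "up to 7 evaluable patients for a total sample size of 10 evaluable biomarker positive patients with that histology". At most three cohorts open, with at most 21 added evaluable patients in total.
- **Verdict on an expansion cohort (11.3).** "Histology-specific biomarker positive expansion cohorts will, by definition, be deemed worthy of further study, since they will have at least 3 responses".
- **Purpose of the expansion (11.3.2).** "This will allow us to estimate more precisely the activity in biomarker positive patients of that histology". Section 11.3 tabulates 90% Wilson intervals for 3, 4 and 5 responses in 10.

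The table of operating characteristics has one row, for the primary cohort. No threshold, alpha, power or futility rule is given for a histology-specific cohort.

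**The concern.** The verdict on an expansion cohort has a single input: whether at least 3 primary-cohort patients of that histology responded. That is already the condition for opening the cohort. Responses cannot be subtracted, so nothing seen in later patients can reverse the verdict. A histology that opens on 3 of 3 and then shows 0 of 7 is still declared worthy of further study.

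Two things are at stake. First, a prespecified success statement would be reported for the expansion although its own patients had no part in it. Second, the result shown beside that statement pools the selecting responses with the new ones. A reader who sees 3 of 10 with an interval above the 5% null may take it as support from the expansion, when all three responses could predate it.

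**Working it through.** **Inputs (Sections 11.1, 11.3, 11.3.1, 11.3.2).** Null rate 5%, target rate 25%, primary N = 20, rule at least 3 responses, total of 10 per histology, at most three cohorts, 15% inevaluable, 90% Wilson intervals. Write m for the number of primary-cohort patients of a given histology. I read the number added as 10 − m, so 7 are added only when m = 3.

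**1. The plan's own figures reproduce.**
- Alpha: P(X ≥ 3 of 20 at 5%) = 1 − (0.95^20 + 20·0.05·0.95^19 + 190·0.05²·0.95^18) = 1 − (0.35849 + 0.37735 + 0.18868) = 7.55%, within the stated 10%.
- Power: P(X ≥ 3 of 20 at 25%) = 90.9%. N = 19 would give 88.9%.
- Wilson limits, with z = 1.645 and z² = 2.706: (p + z²/2n ± z·√(p(1−p)/n + z²/4n²)) / (1 + z²/n). For n = 10 this gives 12.7% to 55.8% at 3 responses, 19.4% to 64.8% at 4 and 26.9% to 73.1% at 5. All match the table.
- Maximum enrolment: (20 + 3·7)/0.85 = 48.2, so 49, as stated.

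**2. The verdict given opening.** At least 3 responses are already counted, so P(worthy | opened) = 100% at any true rate. For m = 3, the chance that none of the 7 new patients responds is (1 − p)^7:

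| True rate | P(0 of 7) | Verdict |
|---|---|---|
| 5% | 69.8% | worthy |
| 10% | 47.8% | worthy |
| 25% | 13.3% | worthy |

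**3. How often a cohort opens falsely.** Any opening needs at least 3 responses among the same 20 patients. If the true rate is 5% in every histology, the chance of any opening is therefore at most 7.55%, however many histologies are present. For one histology with m up to 10, the chance is at most P(X ≥ 3 of 10 at 5%) = 1 − (0.59874 + 0.31512 + 0.07463) = 1.15%. For m = 3 it is 0.05³ = 0.0125%.

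**4. What the pooled 10 show.** Any opened cohort that reaches 10 has at least 3 of 10, so the pooled rate cannot fall below 30%, nor its lower 90% limit below 12.7%. After a 3-of-3 start the expected pooled rate is (3 + 7p)/10:
- at a true 5%: 3.35/10 = 33.5%;
- at a true 25%: 4.75/10 = 47.5%.

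**5. What the new patients alone show.** For 0 of n, the upper 90% Wilson limit is z²/(n + z²):
- n = 7: 2.706/9.706 = 27.9%;
- n = 3: 2.706/5.706 = 47.4%;
- n = 1: 2.706/3.706 = 73.0%.

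**6. A fixed rule of at least 1 new response.** The chance of passing at a true 5% is 1 − 0.95^n. The chance of failing at a true 25% is 0.75^n.

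| New patients | Pass at 5% | Fail at 25% |
|---|---|---|
| 7 (m = 3) | 30.2% | 13.3% |
| 3 (m = 7) | 14.3% | 42.2% |
| 1 (m = 9) | 5.0% | 75.0% |

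**The case against.** The best defence is that the plan discloses the design and gives the expansion a different job. Section 11.3.2 says it is there to estimate activity more precisely, and Section 11.3 supplies the intervals. On that reading one sentence is redundant and nothing is broken. Much of this stands: the purpose is estimation, and the estimate does respond to new data, running from 30% to 100% after a 3-of-3 start. But the same purpose argues against a success declaration that the added data cannot inform.

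A reader might also draw three stronger conclusions that the documents do not support.

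- *The rule inflates false positives.* It does not. The bounds of 7.55% and 1.15% hold without any alpha being stated for a single histology.
- *Up to 21 children are spent on an uninformative cohort.* Their outcomes move the response rate and its interval, and they also count towards the progression-free survival and tolerability aims in Section 1.2. Moreover, 21 is a ceiling. It needs three histologies with exactly 3 primary patients each, all nine responding, which is 45% of the primary cohort and hardly a chance cluster.
- *False openings are common at rates between 5% and 25%.* With m = 9 the opening probability is 5% at a true 10% and 14% at a true 15%, but then only one patient is added. Those figures cannot be combined with the chances of 0 of 7, which apply only when m = 3.

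**Conclusion.** The point holds as a limited design weakness. The histology-specific declaration repeats the opening rule, and patients enrolled after opening cannot change it. The error rate is not at issue, and the primary design is sound. The practical harm lies in reporting: an automatic success label beside a pooled rate that cannot fall below 30% and that, after a 3-of-3 start, averages 33.5% even when the true rate is 5%.

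The conclusion rests on three assumptions. The number added is 10 − m. Patients respond independently at a common rate within a histology. The opening responses stand. On the last, Section 11.5 counts only responses confirmed by central review, while the trigger in 11.3.2 refers to signs of response. If a triggering response were later overturned, the claim of at least 3 responses could itself fail.

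This is a cheap improvement worth making, not a defect that undermines the trial.

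**What to change.** In Section 11.3, delete the sentence that makes the declaration automatic and put in its place wording such as:

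*Opening an expansion cohort nominates a histology. The expansion cohort is for estimation and carries no separate success declaration. The response rate and its 90% Wilson interval will be reported for the patients enrolled after opening alone, and for all 10 patients of that histology.*

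Section 11.3.2 already gives the matching purpose and needs at most a cross-reference.

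Do not substitute a fixed requirement of at least one new response. At a true 25% it would reject 13% of openings with 7 new patients, 42% with 3 and 75% with 1.

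**Cost.** A few sentences, with no extra patients or procedures. The histology loses an automatic label, and the interval for the new patients alone is wide: 0 of 7 gives 0% to 28%, and with fewer patients it is wider still.
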